### **5.4 Preparation and Administration of Study Drug**

The pharmacist will prepare, and dispense the medication sequentially. Medication syringes will be blinded utilizing black tape. Patients will then undergo peripheral nerve block under ultra sound guidance and receive either the study group medication or the control group medication.

### **5.5 Prior and Concomitant Therapy**

All patients will receive no more than 4 mg of midazolam for sedation at the time of the block. All patients will undergo general endotracheal anesthesia using propofol, fentanyl, rocuronium or succinylcholine, sevoflurane in air-oxygen, and ondansetron. Fentanyl will be limited to 250 micrograms intraoperatively. Reversal of muscle relaxant will be with either neostigmine and glycopyrrolate or sugammadex. Block success will be assessed pre-operatively with shoulder abductor weakness and re-assessed on arrival to PACU. Patients will receive a standardized post-operative pain management regimen for 24 hours from PACU arrival.

On the post-operative floor the pain regimen will be standardized according to department protocol as follows:

- Acetaminophen 1000mg Q8 hours scheduled
- Tramadol 50mg Q6 hours PRN pain scale 4-6 with repeat dose
- Tramadol 100mg Q6 hours PRN pain scale 7-10 with repeat dose
- Oxycodone 5mg Q4 hours PRN pain scale 4-6 with repeat dose for pain not controlled with tramadol
- Oxycodone 10mg Q4 hours PRN pain scale 7-10 for pain not controlled with tramadol
- IV Fentanyl 25 mcg Q2hr PRN pain scale 7-10 with repeat dose for pain not controlled with above

Discharge medications will include one of the following options:

1. Oxycodone 5 or 10 mg Q4 hrs PRN for moderate (5-6) to severe (7-10) pain
2. Oxycodone-acetaminophen 5/325 or 10/325 Q4 hrs PRN for moderate (5-6) to severe (7-10) pain, not to exceed 8/day
3. Hydrocodone-acetaminophen 5/325 or 10/325 Q4 hrs PRN for moderate (5-6) to severe (7-10) pain, not to exceed 8/day
4. Tramadol 50 mg or 100 mg Q6 hrs PRN for moderate (5-6) to severe (7-10) pain, not to exceed 6/day
5. Tylenol 1000 mg q6hr PRN pain moderate to severe pain, total dose not to exceed 4000 mg/day

## **5.6 Masking/Blinding of Study**

Patients, care team in recovery, study team members collecting and recording data, and statisticians will be blinded to randomization assignment. The administering anesthesiologist and pharmacy will be unblinded. All patients will be documented in EMR as receiving liposomal bupivacaine to ensure the blind is maintained and to ensure that safety features in the EMR for all patients receiving liposomal bupivacaine are activated. Further, all additional standard precautionary measures (e.g. wrist band) will be similarly implemented for both patient groups.

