### **5.3 Method for Assigning Subjects to Treatment Groups**

Our 110 participants will be equally randomized to one of two treatment arms using a randomized block strategy with varying block sizes. The randomization list will be created in SAS v9.4 (SAS Institute; Cary, NC) and will be uploaded into the REDCap randomization module.

The pharmacy team, the study coordinator, and the statistician will have access to the randomization module with the pharmacy team serving as the primary randomizers and the study coordinator and statistician serving as back-ups. Only the statistician will have knowledge of how the randomization list was built and will be the only one that has seen it.

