#### Handling of Missing Data

Initial descriptive statistics will be performed to quantify univariate missingness and distribution of variables. Observed values that appear to be extreme will be verified with the research staff for accuracy. If extreme values do not appear to exhibit undue influence on the statistical methods they will be kept in the analysis. Otherwise they will be removed. Extreme values found to be erroneous will be corrected.

Missing values for outcomes (e.g. VAS, opioid consumption, etc) will be imputed using the last observation carried forward method. Since we expect downward trends in these observations as time from procedure increases, this method will provide a conservative between-treatment estimate of the effect (assuming the observations are missing at random and are roughly missing with equal frequency within each treatment group).

These results will be compared to the results of a linear mixed-model which doesn't require that every patient has data for every measure at every point in time. Instead, it all information recorded and only excludes those time points at which data is missing. For example, if a patient is missing data at 48 hours, then the linear mixed-model will only include the data at 24 hours and 72 hours. In contrast, the last observation carried forward method would use the observed value from 24 hours for the 48 hour value and then all three time points will be included. In both cases, the baseline values for VAS and opioid consumption must be known for the patient to be included in the analysis.

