#### Multiplicity

There is only one primary hypothesis so we will not adjust for multiplicity at the highest level. However, if the linear mixed-model shows that the time by treatment interaction term is statistically significant and we perform post-hoc pairwise comparisons, the Tukey-Kramer

method will be used to adjust for multiple comparisons. There are several secondary aims that we consider exploratory analyses and as such will not adjust for multiple comparisons.

**Primary Hypothesis:** The average post-op pain score, adjusted for baseline pain scores, over the 72 hours post-op will be significantly lower in the liposomal bupivacaine group.

The difference in post-operative numeric pain scores between the treatment groups over time will be analyzed using a linear mixed-model with an interaction term for time and treatment and will adjust for the baseline (pre-op) scores.

**Secondary Hypothesis 1:** The average post-op satisfaction score over the 72 hours post-op will be significantly lower in the liposomal bupivacaine group.

The difference in post-operative numeric satisfaction scores between the treatment groups over time will be analyzed using a linear mixed-model with an interaction term for time and treatment.

**Secondary Hypothesis 2:** Time to block cessation will be longer in the liposomal bupivacaine group than the standard bupivacaine group.

The difference in time to block cessation will be analyzed between treatment groups using a two sample t-test if necessary model assumptions are met or the Wilcoxon Rank-Sum test if assumptions are not met.

**Secondary Hypothesis 3:** Total opioid consumption will be significantly lower in the liposomal bupivacaine group.

The distribution of total opioid consumption for the two groups will be compared using a multiple linear regression model with a term to adjust for baseline opioid consumption.

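### Section 5.6 says statisticians are blinded, but Section 5.3 gives the statistician the randomization list, module access and a back-up randomizer role

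*Combined protocol and SAP*

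**What the plan says.** Section 5.6 (Masking/Blinding of Study) sets out who is blinded: "Patients, care team in recovery, study team members collecting and recording data, and statisticians will be blinded to randomization assignment". It then names the exceptions: "The administering anesthesiologist and pharmacy will be unblinded". Neither the statistician nor the study coordinator is among them.

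Section 5.3 (Method for Assigning Subjects to Treatment Groups) describes who handles the allocation: "The pharmacy team, the study coordinator, and the statistician will have access to the randomization module". Pharmacy randomizes in the first instance, and the coordinator and the statistician stand in when needed. On the list itself the section adds: "Only the statistician will have knowledge of how the randomization list was built and will be the only one that has seen it".

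Section 7.2 (Handling of Missing Data) leaves a decision to be taken once data are in hand: "Observed values that appear to be extreme will be verified with the research staff for accuracy". Whether a value stays depends on its influence; the text reads "undue influence on the statistical methods they will be kept in the analysis. Otherwise they will be removed".

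Section 6.5 (All Time Points) allows the study coordinator to contact patients who miss electronic surveys and to take the missing data from them directly. A footnote to the Schedule of Events in the same section says pharmacy performs randomization in the pre-operative area.

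**The concern.** The two sections describe the same role in incompatible ways. A person who knows the list and can randomize patients is not blinded to assignment unless some separation is described, and none is. A publication that repeated Section 5.6 would claim a blind that the plan's own procedures do not deliver.

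The blind also has work to do here. The primary outcome is self-reported pain, and the extreme-value rule gives no threshold, does not say who decides and does not require the decision to be made without knowledge of arm. If the statistician makes or advises on those removals, the plan contains a statement of blinding but no mechanism, consistent with Section 5.3, that secures it.

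The coordinator raises a smaller question of the same kind. Section 5.6 blinds those who collect data, yet one person who may collect outcome data is also a stand-in randomizer.

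**Working it through.** This is mainly a comparison of text. The plan gives no figure to reproduce.

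**1. Stated status of the statistician.** Section 5.6 uses the plural, statisticians, and makes no exception for whoever holds the list. Its unblinded group has two members, the administering anesthesiologist and pharmacy.

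**2. What the statistician is given.** Section 5.3 gives three things: knowledge of how the list was built and sight of it, access to the randomization module, and a back-up randomizing role.

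**3. Can both sections stand?** Two readings would reconcile them.
- The list-holder and the analyst are different people. No section says so. Section 7 does not say who runs the analysis and names no second statistician.
- The list was seen but cannot be linked to patients, or carries masked labels. No masked codes or point of unblinding are described, and module access with a back-up role makes a link to patients available.

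**4. Is there a decision for the blind to protect?** Yes: removal of extreme values judged influential (Section 7.2). Erroneous values are dealt with by a separate sentence that has them corrected, so the removal rule can reach genuine observations.

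**5. Scale of one such removal (illustration, not an estimate).**
- From the plan: 50 per arm (Section 3.2); SD 3 and MCID 2 (Section 7.1); VAS every 4 hours in hospital (Section 6.2); two surveys a day after discharge, up to 72 hours (Section 6.3).
- Assumed: a 24 or 48 hour stay, a 0–10 scale, SD 3 applied to patient means, and a patient whose other scores average m, with m between 2 and 6.
- Scores per patient, k: 24/4 + 2×2 = 10 for a 24 hour stay; 48/4 + 1×2 = 14 for a 48 hour stay.
- Deleting one score of 10 lowers the arm mean by (10 − m)/(k × 50).
- With m = 4 and k = 10: 6/500 = 0.012 VAS. Lowest case (m = 6, k = 14): 4/700 = 0.006. Highest case (m = 2, k = 10): 8/500 = 0.016.
- As a share of the MCID: 0.006/2 = 0.3% to 0.016/2 = 0.8%.
- Standard error of the difference: 3 × √(2/50) = 0.6. The shift is therefore about 0.01 to 0.03 standard errors.

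A single pain score moves the result so little that it would not plausibly count as unduly influential, and the plan's own rule would keep it. The arithmetic supports calling the effect small. It does not measure a bias, because the plan does not limit how many values may be removed.

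**6. The coordinator.** Section 5.3 makes the coordinator a back-up randomizer, Section 6.5 lets the coordinator obtain missed outcome data, and Section 5.6 blinds data collectors. These collide only if the coordinator randomizes a patient and later collects that patient's data. Pharmacy is the primary randomizer, and the documents do not say what the module displays. This is a gap, not a contradiction.

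**The case against.** The strongest defence is that the consequence is slight. Pain is reported by patients whose blinding is not in question, the recovery team is also blinded, and no interim analysis is planned (Section 7.2, Interim Analysis), so knowledge of the list cannot drive stopping. It is also normal for a statistician to generate the list, and Section 3.1 calls the trial only single-blinded. Most of this stands, and it limits the weight of the point. It does not remove the conflict: the single-blind label does not cancel the explicit sentence in Section 5.6, and a statistician generating the list becomes a problem only when the same role is also declared blinded.

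A reader might go further than the documents allow in four ways.
- **That the primary result will be biased by a knowable amount.** The documents give no basis for a size, and any simulated removal of single scores rests on assumed stay, correlation and scale, and deletes values the plan would probably retain.
- **That loose analysis rules are part of this contradiction.** The missing threshold for extreme values, and the choice of "two sample t-test if necessary model assumptions are met or the Wilcoxon Rank-Sum test if assumptions are not met" for time to block cessation, would be pre-specification gaps even under perfect blinding. The test choice concerns a secondary hypothesis that the plan treats as exploratory and has no bearing on the primary pain outcome.
- **That the coordinator is routinely unblinded.** Section 5.3 and the Schedule of Events both put pharmacy first, so the route is possible but not usual. Any figure for it would depend wholly on assumed shares.
- **That neutral codes always repair the blind.** They cannot undo the knowledge of someone who has already seen a list with real arm labels.

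**Conclusion.** The point holds. Sections 5.3 and 5.6 cannot both be true of the statistician as written, and no other text reconciles them. It is an internal inconsistency about who is blinded. Generating the list is not in itself a design error.

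It should be corrected, but it does not threaten the trial. The main harm is to the credibility of a stated design feature, with a secondary risk that extreme-value decisions are made with knowledge of arm. Any bias is probably small, on the assumption that few values are removed. The conclusion that the blind is not secured rests on the absence of a named separate analyst, masked codes or a stated point of unblinding. If such an arrangement exists in practice, writing it into the plan would settle the matter.

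For the coordinator, the conclusion is narrower: the data-collector blind is not secured for any patient whom the coordinator randomizes.

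**What to change.** The remedy depends on whether the list already exists.

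- **List not yet generated.** Build it with neutral codes (A/B), with pharmacy, already unblinded, holding the key. Limit module access and back-up randomization to the pharmacy team. Release the key only after data cleaning, extreme-value decisions and analysis choices are locked. Align Section 5.6 with Section 5.3.
- **Statistician has already seen real arm labels.** Restate Section 5.6 so that this statistician is listed as unblinded. Fix and document the extreme-value and analysis-choice decisions before outcome data are linked to arm.
- **In either case.** State that a coordinator who randomizes a patient is unblinded for that patient.

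The first route costs a change of user rights in REDCap, revised wording and slightly less back-up cover for randomization; the documents do not show whether pharmacy alone can provide that cover. It needs no second statistician. The second route costs a less favourable blinding statement. Neither changes the sample size, the endpoints or the treatments.

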# **6 Study Procedures**

## **6.1 Visit 1**

This will be the initial visit when patient elects to undergo total shoulder replacement surgery. Patients who meet inclusion criteria will be given the opportunity to be enrolled in the study if they so choose. A brief survey will be performed by the research assistant to determine if any exclusion criteria are met. Should they elect to partake, they will be consented and assigned to specific treatment groups. Patient pain scales (VAS) and patient reported outcome measures (ASES, SST, SANE, VR-12) will be measured at the pre-operative visit. All patient demographic information and medical history will be obtained as is routine during the pre-operative visit.

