## 2 Study Objectives

The primary outcome measure will be:

1. Mean difference in patient pain scores over the first 72 hours post-operatively between two groups

Secondary outcomes will include:

1. Total opioid consumption (as measured utilizing morphine intravenous equivalents) in first 72 hours and at 3 weeks
2. Patient perceived duration of block determined as the time patient perceives complete resolution of block
3. Patient satisfaction with pain control at 72 hours, 3 weeks post-operatively and patient reported outcome measures (SANE, SST, ASES, VR-12) at 3 weeks post-operatively

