### 6.4 First Post-operative Visit (3-weeks post-op)

During the first follow-up visit, total opioid consumption during their post-operative course will be measured, and pain scales and satisfaction scores will be obtained including ASES, SST, SANE, VR-12. Total opioid consumption will be quantified by the number of narcotic prescription pills remaining. Opioid consumption will be standardized to morphine equivalents. All diaries will be collected at this time.

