## **7.3 Subject Population(s) for Analysis**

Only patients who are randomized into the study and have necessary baseline values for primary and secondary outcomes will be included in the analyses.

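### The last-observation-carried-forward rule is not limited to post-operative values, so applied as written it would fill a missing 3-week PROM with the pre-operative score

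*Combined protocol and SAP*

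**What the plan says.** - **Rule.** Section 7.2, Handling of Missing Data: "Missing values for outcomes (e.g. VAS, opioid consumption, etc) will be imputed using the last observation carried forward method". The list of outcomes is open-ended, and no sentence restricts which earlier observation may be carried.
- **Reason given.** "Since we expect downward trends in these observations as time from procedure increases", the plan expects LOCF to be conservative, provided that data are missing at random and about equally often in each arm.
- **Worked example.** "the last observation carried forward method would use the observed value from 24 hours for the 48 hour value".
- **Who is analysed.** "In both cases, the baseline values for VAS and opioid consumption must be known for the patient to be included in the analysis". Section 7.3 adds: "Only patients who are randomized into the study and have necessary baseline values for primary and secondary outcomes will be included in the analyses". Both require a baseline value. Neither requires a post-operative one.
- **PROMs.** Section 2 lists as a secondary outcome "patient reported outcome measures (SANE, SST, ASES, VR-12) at 3 weeks post-operatively". They are collected at Visit 1 (section 6.1: "Patient pain scales (VAS) and patient reported outcome measures (ASES, SST, SANE, VR-12) will be measured at the pre-operative visit") and at the 3-week visit (section 6.4: "pain scales and satisfaction scores will be obtained including ASES, SST, SANE, VR-12"). The Schedule of Events in section 6.5 marks them at those two visits only.
- **VAS.** It is taken at the pre-operative visit (6.1), every 4 hours in hospital (6.2), and twice daily by survey from discharge to 72 hours (6.3).
- **Models.** Section 7.2 tests the primary hypothesis with a linear mixed model that has the pre-op pain score as a covariate. It gives no hypothesis or model for the PROMs, and it treats the secondary aims as exploratory.

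**The concern.** LOCF needs an earlier observation of the same variable. For a 3-week PROM there is exactly one, and it lies on the other side of both the operation and the randomised block. A score from before treatment cannot differ between arms because of treatment. Each patient filled in this way therefore adds a zero to the arm comparison. If the arms lose different fractions of patients, the general change from before to after surgery leaks into the comparison as an apparent treatment effect.

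The plan's justification does not reach this case. A decline with time since the procedure describes values recorded after the procedure and says nothing about one recorded before it. At stake is the 3-week PROM comparison and, in an unusual pattern of missing data, the LOCF version of the pain analysis.

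**Working it through.** The plan gives no figure for the effect of this rule, so there is none to reproduce. The check traces the rule through the visit schedule and then uses simple algebra.

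**1. Trace for the PROMs.** Observations scheduled before 3 weeks: one, the pre-operative visit (sections 6.1, 6.4 and the Schedule of Events). Every 3-week PROM filled by LOCF therefore equals that patient's pre-op score. If LOCF is confined to post-operative values, it can fill no 3-week PROM at all.

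**2. How many patients.** Sections 3.2 and 7.1 expect 10% attrition among 110 patients. If all of it fell on the 3-week visit, 0.10 × 110 = 11 patients would carry a pre-op score as their 3-week result.

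**3. Effect on the arm difference.** Let b be the mean pre-op score (equal in both arms by randomisation), c the control arm's mean change to 3 weeks, D the true arm difference, and mT and mC the fractions missing in the treatment and control arms. Assume that the missing patients resemble the others in their arm.

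- Treatment mean after LOCF: (1 − mT)(b + c + D) + mT·b
- Control mean after LOCF: (1 − mC)(b + c) + mC·b
- Estimated difference: (1 − mT)(c + D) − (1 − mC)c = (1 − mT)D + (mC − mT)c

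The first term is the shrinkage. The second is the false difference.

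**4. Numbers.** D = 10 points, c = +20 or −20 points and the missing fractions are assumptions. The documents give none of them for the PROMs.

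- Equal missingness, any c: 5% gives 0.95 × 10 = 9.5; 10% gives 0.90 × 10 = 9.0; 20% gives 0.80 × 10 = 8.0.
- 15% treatment v 5% control, c = +20: 0.85 × 10 − 0.10 × 20 = 6.5. With c = −20: 8.5 + 2 = 10.5.
- 5% treatment v 15% control, c = +20: 0.95 × 10 + 0.10 × 20 = 11.5. With c = −20: 9.5 − 2 = 7.5.
- No true effect (D = 0), 15% v 5% either way: 0.10 × 20 = 2 points in size. For an assumed 10-point change it is 1 point.

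**5. VAS.** A pre-op VAS can be carried only until the first post-operative reading exists. Assume 10 scheduled scores over 72 hours, a pre-op VAS of 4 to 7 and a true early post-block VAS of 0 to 2. One missed first reading then raises that patient's 72-hour mean by between (4 − 2)/10 = 0.2 and (7 − 0)/10 = 0.7. If 10% of an arm were affected, the arm mean would move by 0.02 to 0.07, against the clinically important difference of 2 in section 7.1.

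**The case against.** The strongest reply is that the plan nowhere says a pre-operative value will be carried, and that its text points the other way. The reason given for LOCF concerns time after the procedure, the one worked example goes from one post-operative time to another, and the pre-op pain score appears as a covariate rather than as a point in the outcome series. This stands as evidence of intent. It does not close the gap: the rule covers outcomes in general, and a programmer applying it to a 3-week PROM has only one value to carry.

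Second, section 7.2 names VAS and opioid consumption, so the PROMs come in only through the open end of the list. They have no stated model and are exploratory. That limits the consequences, but it also means that no other rule in the plan covers a missing PROM.

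Third, with equal missingness the result is shrinkage toward zero, which fits the plan's description of LOCF as conservative. That is correct. With unequal missingness the error can go either way. The documents do not predict unequal loss: patients and data collectors are blinded (5.6), and the coordinator follows up survey non-responders (6.5). The 15% v 5% split is illustrative only.

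A reader might also infer that the primary pain result is biased or loses power. The documents do not support this. As section 7.2 describes it, the mixed model simply leaves out time points with no data, so it never sees a carried value. With VAS taken every 4 hours in hospital, a patient with no post-operative reading at all should be rare.

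**Conclusion.** The concern holds as a missing restriction in the LOCF rule, and mainly for the 3-week PROMs. Read literally, the rule can only replace a missing 3-week PROM with a pre-surgery score. The (1 − m) shrinkage and the false difference of (mC − mT) times the pre-to-3-week change follow from algebra, given that the missing patients resemble the rest of their arm. The point values rest on assumed changes, effects and missing fractions.

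For VAS the gap is an edge case confined to the LOCF analysis, and no power or bias figure for the primary endpoint is warranted. Section 7.2 does not state plainly whether LOCF or the mixed model is the main analysis, but that is a separate question.

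Two stronger readings should be set aside. The plan does not state that baseline values will be carried; it is silent. Nor is LOCF the only method open to the PROMs: a baseline-adjusted analysis of observed scores works, as does a model that takes the pre-op and 3-week scores as repeated outcomes. The point is worth correcting before unblinding, but it does not threaten the primary conclusion.

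**What to change.** In section 7.2, Handling of Missing Data:

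- State that only post-operative observations may be carried forward, and that the pre-op VAS serves as a covariate only.
- State that LOCF is not used for the 3-week PROMs. Analyse the observed 3-week scores with the pre-op score as covariate. This also supplies the PROM model that the section lacks.
- Report the number of missing values by arm for the PROM and LOCF analyses.

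The cost is a few sentences in the plan and a slightly smaller N: patients without a 3-week PROM leave that analysis, and a patient with no post-operative VAS leaves the LOCF analysis. Section 7.3 would need a matching clause, because it now requires only a baseline value.
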